- ^{c.} Between Week 96 and Week 108, the participant should be contacted for a Telephone Visit on Week 102 as described in Table 3 and Section 7.1.6.1.
- d. Signed consent will be obtained prior to participation in the optional OLE Period. Participants entering from M2951 will sign the ICF at OLE Day 1, and participants entering from Tecfidera will sign at the Week 48 End of Treatment Visit. As the OLE Period was extended beyond Week 96 in Protocol amendment 5, consent will also be obtained at Week 96 to allow OLE Period treatment beyond this point.
- e. A physical examination may be performed at additional chemistry visits at the Investigator's discretion.
- f. The following will be obtained predose: vital signs (Section 7.4.4.1), hematology and chemistry (Table 8), and total Ig levels (IgM, IgA, IgG) (see Section 7.4.5).
- 9. Supplementary LFTs include AST, ALT, alkaline phosphatase, GGT, and bilirubin for participants.

During Week 0 to 96 of the OLE, urine samples for urinalysis will be obtained predose on OLE Day 1 and at Weeks 24, 60, 96, and unscheduled visits. If local urinalysis by dipstick is abnormal, urine microscopy should be performed by a central laboratory. If at least 1+ protein is detected, urine protein/creatinine ratio should be determined.

- Louring Week 0 to 104 of the OLE, urine pregnancy tests will also be performed at home at Week 14, Week 16, Week 20, Week 28, Week 32, Week 40, Week 44, Week 52, Week 56, Week 64, Week 68, Week 76, Week 80, Week 88, Week 92, Week 96, Week 100, and Week 104 for women of childbearing potential. Participants will be supplied with at-home test kits.
- Phone calls: during Week 0 to 104 of the OLE, to be done only if urine pregnancy test is completed at home: The Principal Investigator and/or delegated site staff will call participant at Week 14, Week 16, Week 20, Week 28, Week 32, Week 40, Week 44, Week 52, Week 56, Week 64, Week 68, Week 76, Week 80, Week 88, Week 92, Week 96, Week 100, and Week 104 to confirm completion of home pregnancy testing and discuss results.
- m. The IMP will be dispensed on OLE Day 1 and at indicated visits thereafter.

Table 3 Schedule of Assessments – Optional OLE Period Week 108 up to 384

Activity/ Assessment			Oı	n Treatr	ment Vis	sits: W	eek 10	8 to 384				Unscheduled Visit	OLE End of Treatment ^m	End of Trial Visit [™]
OLE Year	OLE Yea	ar 3	OLE Year	4	OLE	rear 5	OLE	Year 6	OLE	Year 7	OLE Year 8		OLE year 8	

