[figure not shown]

Figure 2 Trial Design – Optional OLE Period

BID=twice a day; D=Day; IMP= investigational medicinal product; MRI=magnetic resonance imaging; OLE=Open-label Extension; QD=once a day.

- a Participants who entered the OLE Period initially received M2951 at 75 mg once daily. After review of the efficacy and safety data from the primary analysis at 24 weeks and the blinded extension analysis at 48 weeks, the optimal tested dose is 75 mg twice daily. Accordingly, once IMP for this dose is available at the study site, participants participating in the OLE Period will either enter the OLE Period on the 75 mg twice daily dose or will be switched to the 75 mg twice daily dose.
 - For participants entering the OLE after receiving M2951 during the 48-week main study, the Week 48 Visit is considered the Day 1 Visit for the OLE period.
- b For participants entering from Tecfidera treatment arm, treatment with M2951 will only commence if a participant who received Tecfidera during the 48-week main study has an absolute lymphocyte count ≥ 800/mm³ following 4 weeks of washout. If the participant does not have an absolute lymphocyte count ≥ 800/mm³ following 8 weeks of washout, he or she will be discontinued from the study.
- c Denotes efficacy visits only. Safety visits will be conducted every 2 weeks during the first 16 weeks of treatment, then monthly during the OLE period until Week 96, then 3-monthly until Week 192, then 6-monthly until Week 384.
- d An interim analysis will be performed at Week 60 of the OLE period. A further interim analysis will be planned at the appropriate time point considering the visits schedule around the time of the trigger for the primary analysis of the Phase III RMS studies.
- e Between Week 96 and Week 384 regular Telephone Visits will occur. See Table 3 for the schedule and Section 7.1.6.1 for details of the Telephone Visits.

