11.6 Definition of baseline and change from baseline

For the purpose of statistical analysis, OLE baseline is defined as the last non-missing measurement (including those collected at an Unscheduled visit) prior to the first dose of IMP during OLE. Study baseline is defined as the last non-missing measurement (including those

collected at an Unscheduled visit) prior to the first dose of IMP in the study. If baseline cannot be defined, then the baseline value will be treated as missing. OLE baseline will be used in OLE tables and both baselines will be displayed in the listings based on DBP+OLE period, unless otherwise specified.

Definition of change from baseline (CFB)

CFB and percent CFB at a given post-baseline visit will be computed as follows:

- CFB = visit value baseline value
- Percent CFB = 100 * (visit value baseline value) / baseline value

At the baseline visit, the CFB will be equal to zero and the percent CFB will be missing.

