11.10 Trial day / Treatment day

Trial day is defined relative to the date of randomization. Treatment day is defined relative to the date of start of treatment (i.e. treatment day 1 is the day of the first dose of IMP). There will be a second start of treatment on the day of first administration of Evobrutinib during OLE labeled OLE Treatment day.

The day before the start date of treatment is defined as treatment day -1, i.e., there is no treatment day zero.

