11.11 Repeated and unscheduled measurements

Repeated and unscheduled measurements are included in the listings. Data collected at both scheduled and unscheduled visits will be used for shift analyses.

By-visit summary statistics should be programmed based on assessments at both scheduled and unscheduled visits. Assessments at unscheduled visits will be included according to the visit windowing approach described below. A by-visit summary table/figure will include a footnote indicating whether assessments from unscheduled visits are included in the analysis.

For by-visit tabulations, in case of multiple assessments (including unscheduled) linked to the same visit, the first available assessment (in chronological order) will be included in the summary of a visit. This rule doesn't apply to baseline where the latest assessment before day 1 or OLE day 1 is taken.

Repeated and unscheduled measurements will be reported in the listings.

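### For by-visit tabulations, SAP 11.11 cuts baseline at day 1 and so excludes the predose Day 1 and OLE Day 1 values that SAP 11.6 accepts; neither rule is given precedence.

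*SAP*

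**What the plan says.** SAP 11.6 is the section that defines baseline, and its cut is the first dose: "OLE baseline is defined as the last non-missing measurement (including those collected at an Unscheduled visit) prior to the first dose of IMP during OLE". The study baseline uses the same construction, starting "Study baseline is defined as the last non-missing measurement", with the first dose in the study as the cut. The section adds "If baseline cannot be defined, then the baseline value will be treated as missing" and sets change from baseline to zero at the baseline visit.

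SAP 11.11 gives a tie-break for by-visit tabulations: where several assessments link to one visit, the first in time is used. It then exempts "baseline where the latest assessment before day 1 or OLE day 1 is taken". This cut is a day, not a dose.

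SAP 11.10 fixes the meaning of that day: "treatment day 1 is the day of the first dose of IMP", with day -1 immediately before it and no day zero.

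The protocol places the relevant samples on the dosing day but ahead of the dose. Table 2, footnote f, for the OLE: "The following will be obtained predose: vital signs", followed by hematology, chemistry and total Ig. Table 1 has main-study Ig drawn predose as well, and Protocol 6.2 has IMP taken after the visit procedures. For participants entering from M2951, Figure 2 footnote a states that "the Week 48 Visit is considered the Day 1 Visit for the OLE period", and Protocol 7.1.6 confirms that they have no separate Week 48 End of Treatment Visit.

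**The concern.** A predose value taken on OLE Day 1 comes before the first OLE dose, so it is baseline under 11.6. It does not come before OLE day 1, so it is not baseline under 11.11. The same applies to Day 1 of the main study. The SAP states no order of precedence, and 11.11 is the more specific text for by-visit tables, so a programmer could follow it in good faith.

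What is at stake is the meaning of the by-visit change-from-baseline columns. With an older baseline, change that occurred in the blinded extension or the Tecfidera washout would be reported as OLE change. The placebo arm shows this most clearly. It was to switch to M2951 after Week 24, so its Week 24 Ig value precedes any M2951, while the same column for the M2951 arms would start from an on-drug value.

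**Working it through.** **Step 1. Check the Ig schedule against the plan's own counts (Protocol Appendix II).**
- Main study, Table 1: Day 1, Weeks 4, 16, 24 and 48 = 5 samples; 5 × 4 mL = 20 mL. Appendix II gives 5 and 20 mL. A Screening sample would make it 6 and 24 mL, so the count confirms that none is planned.
- OLE, Tables 2 and 3: Day 1, Weeks 24, 48, 72 and 96 (5); Weeks 120 to 360 every 24 weeks, (360 − 120)/24 + 1 = 11; End of Treatment (1). Total 17; 17 × 5 mL = 85 mL. Appendix II gives 17 and 85 mL.

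**Step 2. Study baseline for Ig.** Scheduled samples dated before Day 1: 0. Scheduled samples on Day 1, predose: 1. Under 11.6 the Day 1 sample is the baseline. Under literal 11.11 none qualifies, and 11.6 then sets the baseline to missing.

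**Step 3. OLE baseline for former M2951/placebo participants.** OLE Day 1 is the Week 48 visit, study day 336. Under 11.6 the predose value at that visit is used, 0 weeks old. Under literal 11.11 the last scheduled earlier collection in Table 1 is used, with age (336 − day)/7.

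| Parameter | Last scheduled collection before OLE Day 1 | Age of baseline |
|---|---|---|
| Ig, ECG, urinalysis | Week 24 (day 168) | (336 − 168)/7 = 24 weeks |
| EDSS, hematology, vital signs, full chemistry | Week 36 (day 252) | (336 − 252)/7 = 12 weeks |
| Supplemental liver tests | Week 44 (day 308) | (336 − 308)/7 = 4 weeks |

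An unscheduled assessment in between would shorten these ages for the participant concerned.

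**Step 4. OLE baseline for former Tecfidera participants.** They complete the Week 48 End of Treatment Visit, wash out for 4 to 8 weeks, then attend OLE Day 1. Literal 11.11 generally returns the Week 48 value. Lymphocyte count is the exception, because Protocol Table 5 repeats it at the washout visits.

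**Step 5. Where the two rules agree or differ for study baseline.** Hematology, chemistry and MRI are taken at Screening and not on Day 1, so both rules select the same value. EDSS and vital signs are taken at both, so 11.11 would select Screening where 11.6 selects Day 1.

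**Step 6. Compare with the rest of the SAP.**
- The zero change required by 11.6 at the baseline visit would generally fail at OLE Week 0 under literal 11.11.
- In SAP Appendix 3, the immune-cell window table uses Screening only to replace a missing Day 1 value, the reverse of literal 11.11.
- In the same appendix, the OLE Week 0 window for former M2951/placebo participants opens at main-study day 189 for Ig and ECG and at day 294 for EDSS. The values that literal 11.11 would select (days 168 and 252) lie outside those windows.

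**The case against.** The strongest reply is that 11.11 does not set out to define baseline. Section 11.6 does, under that title. The 11.11 sentence only exempts baseline from a first-in-time rule; its working content is to take the latest value, not the first, which agrees with 11.6, and its reference to day 1 may be shorthand for the start of treatment. Step 6 supports this, and a reading that leaves Ig with no study baseline is unlikely to be intended. This stands as evidence of intent, so the wording is probably loose drafting. It does not remove the conflict, because 11.10 gives day 1 an exact meaning and no text ranks the two sections.

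The reply also limits the scope, and that part stands. A reader might infer that every OLE change-from-baseline output is affected. The documents do not support that: the 11.11 sentence is confined to by-visit tabulations, so the laboratory and vital-sign shift tables, the QTcF change categories and the Kaplan-Meier outputs conditioned on baseline grade rest on 11.6. A reader might also infer that OLE Day 1 data are discarded. They are not; they remain in the OLE Week 0 rows and in the listings. Finally, SAP 16 describes the efficacy analyses as descriptive with no hypothesis testing, so no confirmatory result is involved.

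**Conclusion.** The two sections specify different baselines for by-visit tabulations, and 11.11 as written selects the wrong one. The size is conditional on literal programming of 11.11 and on visits held as scheduled: an OLE baseline 24, 12 or 4 weeks old for former M2951/placebo participants, a pre-washout baseline for former Tecfidera participants apart from lymphocyte count, and no scheduled Ig sample eligible as study baseline.

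It would be too strong to say that the Ig study baseline does not exist. The Day 1 predose sample is planned and qualifies under 11.6. The output most exposed is the planned set of line plots of median percent change in Ig over the double-blind and OLE periods combined. That exposure rests on two assumptions: that these plots use study baseline, since the SAP there says only baseline, and that 11.11's by-visit rule extends to figures.

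**What to change.** In SAP 11.11, replace the clause "baseline where the latest assessment before day 1 or OLE day 1 is taken" with a cross-reference, for example: *baseline, for which the value defined in Section 11.6 (last non-missing assessment before the first dose, or the first OLE dose, of IMP) is used.*

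Optionally, add that Day 1 and OLE Day 1 assessments that the protocol schedules predose, and that have no recorded time, are treated as predose. This goes beyond resolving the conflict, but it settles how the 11.6 rule is applied when times are missing.

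The cost is one sentence in the SAP, or two with the option, and a check that the baseline derivation follows 11.6. No new data are needed.

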11.12 Early treatment termination assessments

By-visit summary statistics should be programmed based on assessments slotted according to the visit windowing approach described below. A by-visit summary table/figure will include a footnote indicating whether assessments from early treatment termination visits are included in the analysis based on slotting the assessment into the appropriate analysis visit window. The summary for the Early Treatment Termination visit (for assessments not slotted according to a visit window approach) will be distinguished from the OLE Week 384 visit, and the Early Study Termination visit from the summary for the OLE Week 388 visit.

For analyses by time period, data from Safety Follow-up will be included in the period in which the participant has discontinued. Data from Safety Follow-up will also be included in shift table to derive worst grade or value.

11.13 Analysis visit windows

Assessments may be made at times other than the nominal times of planned visits, due to participant scheduling issues, unscheduled visits, or early treatment termination visits.

Analysis visit windows for efficacy and safety endpoints, will be used to incorporate unscheduled assessments in by-visit summaries. For participants discontinuing treatment during the OLE, the premature End of Treatment (EOT) assessment will be windowed appropriately, prior to the analysis, for safety.

For the calculation of analysis visit using the time windows, 1 month is expressed as 30 days.

As the schedule of assessments is different for each visit, specific time windows must be used for each endpoint. They are defined in Appendix 19.3.

For all biochemistry parameters, the same schedule of assessment is considered with all visits possible per protocol.

If there are multiple assessments within a same visit window, then the one closest to the target day will be used. If 2 assessments have the same difference with target day, the earlier one will be used.

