Study Week	W 0	W 1	W 2	W 3	W 4	W 5	W 6	W 7	W 8	W 9	W 10	W 11	W 12	W 13	W 14		W16, W20	W 24	W28, W32	W 36	W40, W44		W52, W56	W 60	W64, W68	W 72	W76, W80	W 84	W88, W92	W 96°	
Study Day ± Visit Window	1 ±3	±3	±3	±3	28 ±7	±3	±3	±3	56 ±7	±3	±3	±3	84 ±7	±3	±3	±3	±3	168 ±7	±3	252 ±7	±3	336 ±7	±3	420 ±7	±3	504 ±7	±3	588 ±7	±3	672 ±7	
CCI																														Х	
Urine pregnancy test (all countries) ^{k,l}	х				х				х				Х		х		Х	Х	Х	х	х	х	Х	Х	Х	Х	Х	Х	Х	Х	
12-lead ECG	Х																					Χ								Χ	Х
Chest X-ray	Χ																														
EDSS	Χ																					Х								Х	Х
Relapse assessment	Х	Х	X	Х	Х	Х	Х	Х	Х	Х	Х	Х	X	Х	Х	Х	Х	Х	Х	Х	Х	Х	Х	X	Х	X	Х	X	Х	Х	Х
MRI scan	Χ																					Х								Х	
Concomitant medications and procedures	Х	Х	X	Х	Х	х	X	х	Х	X	х	Х	X	Х	X	Х	Х	Х	Х	Х	Х	Х	Х	X	Х	X	Х	X	Х	X	х
AE evaluation	Χ	Χ	Χ	Χ	Х	Χ	Χ	Χ	Χ	Χ	Х	Χ	Χ	Χ	Χ	Χ	Х	Х	Х	Х	Х	Х	Х	Х	Х	X	Х	Х	Х	Χ	Х
Dispense IMP ^m	Х				Х				Х				Χ					Χ		Χ		Х		Χ		Χ		Χ		Х	
IMP compliance	Х				Х				Х				Χ					Χ		Χ		Х		Χ		Χ		Χ		Х	
CCI																															
C-SSRS (Since Last Visit Scale)	Х																					Х								Х	

CONFIDENTIAL INFORMATION

32/131

Global Version ID: 78691_4737384_6296959

AE=adverse event, ALT=alanine aminotransferase, AST=aspartate aminotransferase, CCI , CMV=cytomegalovirus, C-SSRS=Columbia-Suicide Severity Rating Scale, EA=early antigen, EBNA=Epstein-Barr nuclear antigen, ECG=electrocardiogram, eCRF=electronic case report form, EDSS=expanded disability status scale, ESR=erythrocyte sedimentation rate, GGT=γ-glutamyl-transferase, HAV=hepatitis A virus, HBc=hepatitis B core antigen, HEV=hepatitis E virus, CCI , hsCRP=high sensitivity C-reactive protein, ICF=informed consent form, Ig=immunoglobulin, IMP=investigational medicinal product, INR=international normalized ratio, LFT=liver function test, MRI=magnetic resonance imaging, MS=multiple sclerosis, VCA=viral capsid antigen.

- a. As described in Section 7.1.6, there may be a dosing delay between Visit 11 (Week 96) and Visit 12 (Week 108). In this circumstance, the participant should return to the study site when dosing resumes, and the procedures described in Section 7.1.6 should be performed.
- b. Visits 2 (Week 4) and 3 (Week 8) are applicable only for participants who received Tecfidera, and for participants who received M2951/placebo these visits are only for LFTs (Section 7.1.6 and Section 7.1.3).

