Protocol-specified clinical laboratory hematology, biochemistry and urinalysis parameters will be summarized using descriptive statistics appropriate to continuous-valued random variables (see Section 11.5) by time point and by treatment group during the OLE period. At each time point, both observed value and CFB value will be summarized.

Graphical Display of Clinical Laboratory Data

Boxplots of laboratory values by treatment group and timepoint will be provided for the hematology and biochemistry parameters displayed in Table 4.

Table 4: Parameters for boxplots

Category	Laboratory parameter	Conventional Unit	SI Units
	Hemoglobin	g/dL	g/L
	Red blood cell count	$10^6/\mu L$	$10^{12}/L$
	Reticulocyte count	$10^3/\mu L$	10 ⁹ /L
Hematology	White blood cell count	$10^3/\mu L$	10 ⁹ /L
Tenmorogy	Neutrophil count	$10^3/\mu L$	10 ⁹ /L
	Lymphocyte count	$10^3/\mu L$	10 ⁹ /L
	Eosinophils	10 ⁹ /L	10 ⁹ /L
	Basophils	10º/L	10 ⁹ /L
	Platelet count	$10^3/\mu L$	10 ⁹ /L
	Alanine aminotransferase (ALT)	U/L	U/L
	Albumin	g/dL	g/L
	Aspartate aminotransferase (AST)	U/L	U/L
	Gamma- glutamyl transferase (GGT)	U/L	U/L
Biochemistry	Alkaline phosphatase	U/L	U/L
	Total bilirubin	mg/dL	μmol/L
	Amylase	U/L	U/L
	Lipase	U/L	U/L
	eGFR	mL/min	mL/min
	Blood urea nitrogen (BUN)	mg/dL	mmol/L
	Creatinine	mg/dL	μmol/L
	Glucose	mg/dL	μmol/L
	Sodium	mEq/L	mmol/L
	Potassium	mEq/L	mmol/L

Boxplots will be displayed from the OLE Baseline up to OLE Week 48 and from OLE Week 52 to OLE Week 96 etc. to remain readable.

The ULN and LLN will be added to the lab parameter boxplot, for any lab parameter where the normal range is the same for all participants in the analysis set. All graphical displays will be shown on a log-scale when needed to make the plot readable. All plots of a given parameter will have the same scale to allow comparison between groups and periods.

Liver function tests

AST, ALT and total bilirubin are used to assess possible drug induced liver toxicity. The ratios of test result over upper limit of normal (ULN) will be calculated and classified for these 3 parameters during the OLE period.

Summary of liver function tests will include the following categories. The number and percentage of participants with each of the following categories during the OLE period will be summarized by treatment group:

- AST $\geq 3 \times ULN$, AST $\geq 5 \times ULN$, AST $\geq 10 \times ULN$, AST $\geq 20 \times ULN$
- ALT \geq 3×ULN, ALT \geq 5×ULN, ALT \geq 10×ULN, ALT \geq 20×ULN

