19.3 Appendix 3: Analysis visit windows for Safety and Efficacy Endpoints

Analysis visit windows for biochemistry parameters through OLE Period

Analysis visit	Nominal analysis visit	Analysis visit window (days)	
	day	Evobrutinib/Placebo	Tecfidera during
		during main study	main study
OLE Week 0	1	[1, 1]	[1, 1]
OLE Week 1	7		[2, 11)
OLE Week 2	14	[2, 21)	[11, 18)
OLE Week 3	21		[18, 25)
OLE Week 4	28	[21, 35)	[25, 32)
OLE Week 5	35		[32, 39)
OLE Week 6	42	[35, 49)	[39, 46)
OLE Week 7	49		[46, 53)
OLE Week 8	56	[49, 63)	[53, 60)
OLE Week 9	63		[60, 67)
OLE Week 10	70	[63, 77)	[67, 74)
OLE Week 11	77		[74, 81)
OLE Week 12	84	[77, 91)	[81, 88)
OLE Week 13	91		[88, 95)
OLE Week 14	98	[91, 105)	[95, 102)
OLE Week 15	105		[102, 109)
OLE Week 16	112	[105, 126)	[109, 126)
OLE Week 20	140	[126, 154)	•
OLE Week 24	168	[154, 182)	
OLE Week 28	196	[182, 210)	
OLE Week 32	224	[210, 238)	
OLE Week 36	252	[238, 266)	
OLE Week 40	280	[266, 294)	
OLE Week 44	308	[294, 322)	
OLE Week 48	336	[322, 350)	
OLE Week 52	364	[350, 378)	
OLE Week 56	392	[378, 406)	
OLE Week 60	420	[406, 434)	
OLE Week 64	448	[434, 462)	
OLE Week 68	476	[462, 490)	
OLE Week 72	504	[490, 518)	
OLE Week 76	532	[518, 546)	
OLE Week 80	560	[546, 574)	

Analysis visit	Nominal analysis visit		days)
	day	Evobrutinib/Placebo during main study	Tecfidera during main study
OLE Week 84	588	[574, 602)	•
OLE Week 88	616	[602, 630)	
OLE Week 92	644	[630, 658)	
OLE Week 96	672	[658, 714)	
OLE Week 108	756	[714, 798)	
OLE Week 120	840	[798, 882)	
OLE Week 132	924	[882, 966)	
OLE Week 144	1008	[966, 1050)	
OLE Week 156	1092	[1050, 1134)	
OLE Week 168	1176	[1134, 1218)	
OLE Week 180	1260	[1218, 1302)	
OLE Week 192	1344	[1302, 1428)	
OLE Week 216	1512	[1428, 1596)	
OLE Week 240	1680	[1596, 1764)	
OLE Week 264	1848	[1764, 1932)	
OLE Week 288	2016	[1932, 2100)	
OLE Week 312	2184	[2100, 2268)	
OLE Week 336	2352	[2268, 2366)	

Analysis visit windows for biochemistry parameters through DBP

Analysis visit	Nominal analysis visit day	Analysis visit window (days)
		All treatment groups
Day 1	1	[1, 1]
Week 4	28	[2, 42)
Week 8	56	[42, 63)
Week 10	70	[63, 77)
Week 12	84	[77, 91)
Week 14	98	[91, 105)
Week 16	112	[105, 119)
Week 18	126	[119, 133)
Week 20	140	[133, 147)
Week 22	154	[147, 161)
Week 24	168	[161, X ^[1]]
Week 26	182	(X ^[1] , X ^[1] + 21)
Week 28	196	[X ^[1] + 21, X ^[1] + 35)
Week 30	210	[X ^[1] + 35, X ^[1] + 49)
Week 32	224	[X ^[1] + 49, X ^[1] + 63)
Week 34	238	[X ^[1] + 63, X ^[1] + 77)

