Analysis visit windows for vital signs through OLE Period

Analysis visit Nominal analysis		Analysis visit window (days)	
	visit day	Evobrutinib/Placebo	Tecfidera during
		during main study	main study
OLE Week 0	1	[1, 1]	[1, 1]
OLE Week 4	28		[2, 42)
OLE Week 8	56		[42, 70)
OLE Week 12	84	[2, 126)	[70, 126)
OLE Week 24	168	[126, 210)	
OLE Week 36	252	[210, 294)	
OLE Week 48	336	[294, 378)	
OLE Week 60	420	[378, 462)	
OLE Week 72	504	[462, 546)	
OLE Week 84	588	[546, 630)	
OLE Week 96	672	[630, 714)	
OLE Week 108	756	[714, 798)	
OLE Week 120	840	[798, 882)	
OLE Week 132	924	[882, 966)	
OLE Week 144	1008	[966, 1050)	
OLE Week 156	1092	[1050, 1134)	
OLE Week 168	1176	[1134, 1218)	
OLE Week 180	1260	[1218, 1302)	
OLE Week 192	1344	[1302, 1428)	
OLE Week 216	1512	[1428, 1596)	
OLE Week 240	1680	[1596, 1764)	
OLE Week 264	1848	[1764, 1932)	

Analysis visit	Nominal analysis	Analysis visit window (days)	
	visit day	Evobrutinib/Placebo during main study	Tecfidera during main study
OLE Week 288	2016	[1932, 2100)	
OLE Week 312	2184	[2100, 2268)	
OLE Week 336	2352	[2268, 2366)	

Analysis visit windows for EDSS through DBP

Analysis visit	Nominal analysis visit day	Analysis visit window (days)
		All treatment groups
Day 1	1	[1, 1]
Week 12	84	[2, 126)
Week 24	168	[126, 189)
Week 36	252	[189, 294)
Week 48	336	[294, 339)

Analysis visit windows for EDSS through OLE Period

[figure not shown]
Analysis visit	Nominal analysis visit	Analysis visit window (days)
	day	All treatment groups
OLE Week 0	1	[Main period day 294, OLE 169]
OLE Week 48	336	[169, 504)
OLE Week 96	672	[504, 840)
OLE Week 144	1008	[840, 1176)
OLE Week 192	1344	[1176, 1512)
OLE Week 240	1680	[1512, 1848)
OLE Week 288	2016	[1848, 2184)
OLE Week 336	2352	[2184, 2382)

[figure not shown]
Analysis visit windows for MRI through OLE Period

Analysis visit	Nominal analysis visit	Analysis visit window (days)
	day	All treatment groups
OLE Week 0	1	[Main period day 189, OLE 30)
OLE Week 48	336	[30, 504)
OLE Week 96	672	[504, 840)
OLE Week 144	1008	[840, 1176)
OLE Week 192	1344	[1176, 1512)
OLE Week 240	1680	[1512, 1848)
OLE Week 288	2016	[1848, 2184)
OLE Week 336	2352	[2184, 2382)

[figure not shown]
CCI	
CCI	

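### The OLE biochemistry windows follow the liver-test schedule for every chemistry parameter, so non-liver tests get by-visit rows at weeks when none is scheduled, and some former-Tecfidera samples are labelled to an adjacent week

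*SAP*

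**What the plan says.** SAP 11.13 first sets a general principle, "As the schedule of assessments is different for each visit, specific time windows must be used for each endpoint", and then makes an exception for chemistry: "For all biochemistry parameters, the same schedule of assessment is considered with all visits possible per protocol". Appendix 3 carries this out in one table, headed "Analysis visit windows for biochemistry parameters through OLE Period". Its windows are weekly to Week 16 for former Tecfidera participants, two-weekly to Week 16 for the others, and four-weekly from there to Week 96.

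The protocol does not draw the full panel that often. Table 2 schedules clinical chemistry at OLE Weeks 0, 4, 8, 12, 24, 36, 48, 60, 72, 84 and 96. Footnote b restricts Weeks 4 and 8: "for participants who received M2951/placebo these visits are only for LFTs". Footnote g defines what the supplemental safety visits measure: "Supplementary LFTs include AST, ALT, alkaline phosphatase, GGT, and bilirubin for participants". The LFT-visit row of Table 8 lists the same five tests.

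The by-visit outputs cover all chemistry. SAP 17.3 says "Protocol-specified clinical laboratory hematology, biochemistry and urinalysis parameters will be summarized using descriptive statistics appropriate to continuous-valued random variables", by time point, as observed value and change from baseline. Of the 14 biochemistry parameters in its boxplot list (Table 4), nine are not liver-visit tests: albumin, amylase, lipase, eGFR, BUN, creatinine, glucose, sodium and potassium. SAP 11.11 adds "By-visit summary statistics should be programmed based on assessments at both scheduled and unscheduled visits". SAP 11.13 also places premature end-of-treatment samples into the windows. SAP 11.5 counts a participant who is still in the trial but has no value at a time point as missing.

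**The concern.** A by-visit row is normally read as a picture of the group at that week. For a test that is not scheduled at that week, the row shows whoever happened to be sampled, and sampling depends on a retest, a suspected relapse, an early stop or an off-target visit. Its mean, change from baseline and boxplot sit beside rows holding the whole group. SAP 17.3 starts the second boxplot panel at OLE Week 52, itself a liver-test-only week.

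The second issue is the week label. Former Tecfidera participants are the only ones new to evobrutinib in the OLE, so their Week 4, 8 and 12 chemistry is the early-exposure picture. Their windows are narrower than the visit tolerance the protocol gives those visits. Amylase and lipase elevation is an adverse event of special interest (SAP 17.2.3), so its by-visit display should be readable.

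**Working it through.** The plan gives no figure of its own here, so the check sets the SAP windows against the protocol schedule.

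**Inputs.** Windows: SAP Appendix 3, OLE biochemistry table. Full-panel weeks: Protocol Table 2 with footnote b, and Table 3 after Week 96. Tolerance: Table 2 allows ±7 days at Weeks 4, 8 and 12 (Days 28, 56 and 84).

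**Step 1: rows with no scheduled non-liver chemistry.**

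| | Windows to Week 96 | Full-panel weeks to Week 96 | Without | Windows, whole OLE |
|---|---|---|---|---|
| Former M2951/placebo | 29 | 9 (0, 12, 24, …, 96) | 29 − 9 = 20 | 29 + 14 = 43 |
| Former Tecfidera | 37 | 11 (also 4 and 8) | 37 − 11 = 26 | 37 + 14 = 51 |

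The 14 later windows (Weeks 108 to 336) all have scheduled full chemistry. Over the whole table the shares are 20/43 = 47% and 26/51 = 51%.

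**Step 2: week labels for former Tecfidera.**

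| Visit | Permitted days | SAP window | Days labelled elsewhere |
|---|---|---|---|
| Week 4 | 21–35 | [25, 32) | 21–24 to Week 3; 32–35 to Week 5 |
| Week 8 | 49–63 | [53, 60) | 49–52 to Week 7; 60–63 to Week 9 |
| Week 12 | 77–91 | [81, 88) | 77–80 to Week 11; 88–91 to Week 13 |

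At each visit, 7 of 15 permitted days keep the right label and 8 of 15 do not. The share of samples affected depends on how visit days are distributed, which the documents do not give. If they are spread evenly it is 8/15 = 53%. If they are normal around target with SD 3 days, rounded to whole days and cut at ±7, it is (0.988 − 0.757)/0.988 = 23%, where 0.988 = P(|Z| < 7.5/3) and 0.757 = P(|Z| < 3.5/3). Samples within 3 days of target are labelled correctly. For former M2951/placebo, only Day 91 at Week 12 moves (1 of 15, to Week 14).

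**Step 3: what can enter the unscheduled rows.**
- Chemistry from unscheduled neurological-worsening visits (Protocol 7.1.4).
- Premature end-of-treatment samples (SAP 11.13).
- The displaced routine samples from Step 2.
- Some retests. Protocol 6.4.4.1 asks for amylase, lipase and creatinine rechecks within 24 hours of receipt, and these mostly stay in the index window. It also allows retesting within a week in other cases, and follow-up after a laboratory-related discontinuation. A retest 7 days after an on-target Week 12 sample is Day 84 + 7 = 91, which is the Week 14 window [91, 105).

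**Step 4: the vital-sign windows as the alternative.** The table headed "Analysis visit windows for vital signs through OLE Period" has rows only at full-panel weeks: 43 − 20 = 23 and 51 − 26 = 25. For former Tecfidera, [2, 42), [42, 70), [70, 126) and [126, 210) contain all permitted days at Weeks 4, 8, 12 and 24, so 0 of 15 are misplaced at each. One gap remains at Week 336: Day 2352 + 14 = 2366, but the window is [2268, 2366). The current biochemistry table has the same gap.

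**The case against.** The strongest reply is that the consequences are modest and visible. Tables show non-missing and missing counts, and by-visit outputs carry a footnote on whether unscheduled samples are included, so a very small row would be noticed. Worst-value and worst-grade shift tables, the Kaplan-Meier outputs, the Grade 3 or higher listings and the special-interest summaries do not use the week label. There is no hypothesis test. All of this stands and limits the weight of the point.

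A reader might infer that these rows contain nothing but rechecks of abnormal values and would therefore show spurious spikes. The documents do not support that. Other samples enter (Step 3), and prompt rechecks rarely leave the index window. From Week 24 to Week 84 the full-panel windows run from 14 days before target to 13 days after, so a recheck after an on-target visit would have to come at least 14 days later to reach the next row. Nor can the distortion of a mean be sized, because the protocol gives no repeat-recheck interval.

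A reader might also say that former-Tecfidera values are lost. They are not: a Day 33 sample moves to Week 5, whose target, Day 35, is closer. Nearest-day labelling is ordinary practice. The difficulty is that the neighbouring row has no scheduled non-liver sample.

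Finally, Protocol 7.1.3 describes the extra chemistry as including the five liver tests, which leaves slight room for a fuller panel. Table 2 footnote g and Table 8 list only the five.

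**Conclusion.** The point holds and should be corrected, with its effect confined to descriptive OLE by-visit tables and boxplots. Through Week 96, 20 of 29 windows (former M2951/placebo) and 26 of 37 (former Tecfidera) have no scheduled non-liver chemistry. It would be wrong to say that most rows of the whole OLE table are affected in both groups, since the shares there are 47% and 51%, and no row after Week 96 is affected. In the affected rows, non-liver results would be few and non-randomly sampled, with nearly everyone shown as missing for a test that was never due.

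The label shift applies at three visits in one former arm, and only to samples 4 to 7 days off target.

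The counts rest on reading the supplemental visits as limited to the five liver tests. The 53% and 23% rest on assumed visit-day distributions; the 8 of 15 days does not.

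**What to change.** In SAP 11.13 and Appendix 3, restrict the present OLE biochemistry windows to AST, ALT, ALP, GGT and total bilirubin. For all other OLE chemistry parameters, use the vital-sign windows:

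- Former Tecfidera: Week 4 [2, 42), Week 8 [42, 70), Week 12 [70, 126).
- All others: Week 12 [2, 126).
- Both groups: Week 24 [126, 210), Week 36 [210, 294), and onward as tabulated.
- Week 336: extend the upper bound so that Day 2366 is included.

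This removes the unscheduled rows for non-liver tests and brings misplaced permitted days at Weeks 4, 8, 12 and 24 to 0 of 15. It does not change the labelling of the liver tests themselves. An off-target Week 4, 8 or 12 liver sample would still move one week, but into a row where liver tests are scheduled.

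The cost is a short SAP wording change and one parameter-specific window lookup in the laboratory analysis dataset. No new data are needed.
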